5.2.1.1.2 Dose Selection in Part II - Expansion Cohorts (Cohorts A and B)

The starting dose for Cohorts A and B is confirmed to be based on the safety, PK, and PD data from dose escalation and confirmation of MK-1454 IT in combination with pembrolizumab in Arm 2 (Table 8). The minimum number of lesions per subject per treatment visit to be injected is 1 lesion, and the maximum number of lesions to be injected per subject per treatment visit is 3 lesions. Each subject at this dose level will receive a fixed dose of intratumoral MK-1454 prepared in a volume of 1 mL to 3 mL of injectate, based on lesion size (see Table 9).

The starting dose for Cohort C will be the preliminary RP2D (both dose level and frequency) from the dose escalation and confirmation of MK-1454 visceral IT established in combination with pembrolizumab in Arm 3.

Dose volume for Expansion Cohorts will be determined by lesion size, as detailed in Table 9.

Protocol/Amendment No.: 001-08

Table 8 Trial Treatment for MK-1454 IT in Combination with Pembrolizumab Part II (Expansion Cohorts A, B, and C)

Drug, Vaccine, Biologic, Device, etc.	Dose/ Potency	Dose Frequency	Route of Administration	Regimen/ Treatment Period	Use
Pembrolizumab	200 mg	Q3W	IV infusion	Day 1 of each 21-day cycle	Experimental
MK-1454ª	Cohorts A and B: Colort C: Preliminary RP2D established in Arm 3	Cohorts A and B: CCI Cohort C: TBDb	Intratumoral Via visual inspection for cutaneous lesions, or via ultrasound or cross-sectional imaging (CT/MRI) guidance, as needed	Cohorts A and B: CCI Cohort C: TBDb	Experimental

CT = computed tomography; MTD/MAD = maximum tolerated dose/maximum administered dose; MRI = magnetic resonance imaging; QW = once each week; Q3W = once every 3 weeks; RP2D = Recommended Phase 2 Dose; TBD = to be determined.

Table 9 Injectate Volume for Arm 3 Visceral IT (Part I) and Expansion Cohorts (Part II)

Lesion Size (longest dimension)	Injection Volume
>5 cm	3 mL
>2.5 cm to 5 cm	2 mL
≥1.0 cm to 2.5 cm	1 mL

5.2.1.2 Accelerated Titration Design in Arms 1, 2, and 3

The initial dose escalation in Arms 1, 2, and 3 will proceed following an ATD.

Single subjects will be enrolled into sequential dose levels with up to 300% dose increment increases from the previous dose, eg Dose ranges are outlined in Table 3, Table 4, and Table 5. Up to 3 subjects per cohort may be allowed in the event of simultaneous enrollment. The first 2 subjects who will receive MK-1454 treatment at a new dose level must be at least 7 days apart. The subsequent dose level to be tested in the next cohort of subjects will be communicated to the investigator or designee following each dose escalation decision meeting.

The dose for ending ATD will be the dose level at which one of the following occurs:

- The cohort is completed.
- ≥ Grade 2 toxicity as assessed by the investigator to be related, probably related, or possibly related to the drug according to NCI CTCAE v4.

^a MK-1454 will be administered within 0.5 to 4 hours following completion of pembrolizumab infusion.

^b Dose frequency will be determined in Arm 3.

Protocol/Amendment No.: 001-08

• Elevation of systemic TNF- α in blood above baseline levels by ≥ 3 -fold in a given subject during the first cycle of MK-1454 (Arm 1 and 2 only).

5.2.1.3 Dose Escalation and Confirmation During Modified Toxicity Probability Interval Design

Dose escalation and confirmation of MK-1454 will proceed from ATD phase (Part A, Part C, or Part E) to mTPI phase (Part B, Part D, or Part F) once at least 1 of the 3 triggering criteria is met (see Section 2.1) [31]. Subjects will be enrolled via IWRS according to the dose escalation and confirmation guidelines outlined in Section 5.2. The target DLT rate is 30%, with a tolerance interval of 3%. The specific dose levels for the ATD and mTPI phases will be determined through emerging safety and toxicity data. For the mTPI phase, dose escalation will proceed at dose increments between 30% and 100% of the prior dose level. The dose to be tested in the next cohort of subjects will be communicated to the investigator or designee following each dose escalation decision meeting. Depending on the accrual rate, there may be a minimum of 3 and up to 6 subjects enrolled within 21 days of initiation at each new dose level. The first 2 subjects in each new dose level will receive MK-1454 treatment at least 7 days apart. Based on the occurrence of DLTs, up to 14 subjects may enroll per dose level. Enrollment will be monitored through IWRS.

Dose escalation based on the mTPI design will be conducted according to Table 10, which provides the rules for determining the next dose [32] [33]. In Table 10, the columns show the number of patients treated at a dose level, and the rows correspond to the number of subjects who experience a DLT. The entries of the table are dose-finding decisions: E, S, D, and DU, which represent the following parameters: Escalating the dose, Staying at the same dose, De-escalating the dose, and excluding the Dose from the trial due to Unacceptable toxicity. For example, if 0 out of the first 3 subjects in a given dose level develop a DLT, then the dose can escalate to the next level without further expansion. If 2 subjects out of the first 3 subjects develop a DLT, then the dose will be de-escalated to the next lower dose level. If 3 out of the first 3 subjects develop a DLT, then this indicates an unacceptable toxicity. If 1 out of the first 3 subjects of a given dose level develops a DLT, then the current dose level cohort will be expanded by continuing enrollment according to Table 10. The same principle will be applied whether 3, 4, 5 or 6 subjects are initially enrolled in the same dose cohort according to Table 10.

The number of subjects who are enrolled at each dose is capped to minimize the exposure to a dose that may be unacceptably toxic (denoted as DU in Table 10). To find out how many more subjects may be enrolled, count steps in a diagonal direction (down and to the right) from the cell (3 subjects, 1 DLT) to the first cell marked DU. For example, if 1/3 of the subjects have experienced a DLT at a given dose level, then no more than an additional 3 subjects should be enrolled at this dose level until additional DLT data are available. This is because this dose level would be considered unacceptably toxic if all 3 of the additional subjects experience a DLT (ie, 4/6 subjects with DLT in Table 10).

De-escalation (D) or excluding the dose from the trial due to unacceptable toxicity (DU) at the starting dose level of Arm 1 of the study indicates stopping of the trial. Escalation (E) at the highest dose level indicates staying at that level. During dose escalation and confirmation, it may be acceptable to de-escalate to an intermediate, not predefined and not

Protocol/Amendment No.: 001-08

previously-studied dose if evaluation of toxicity at such a dose is desired. If this approach is taken, 3-6 new subjects may be enrolled at the new intermediate dose, and the aforementioned rules should be used to determine further enrollment at this dose level. After 14 subjects have been enrolled at any of the tested doses (including intermediate doses), dose finding will stop if the mTPI table indicates "S" for staying at current dose. Otherwise, up to 14 new subjects may be enrolled at a lower dose if "D" or "DU" is indicated, or at a higher dose if "E" is indicated. Establishment of the MTD/MAD for the combination of MK-1454 and pembrolizumab in Arm 2 requires that at least half of the 14 subjects in the MTD/MAD cohort have had no prior exposure to MK-1454 (ie, non-crossover subjects). Priority for enrollment in the MTD/MAD confirmation cohort of Arm 2 will be given to MK-1454-naïve subjects.

While the mTPI design is applied separately to Arm 1 and Arm 2, doses of MK-1454 used in combination with pembrolizumab via cutaneous or subcutaneous IT injection will be at least 2 dose levels behind the MK-1454 monotherapy dose, and will not exceed the MTD for monotherapy. If an MTD for monotherapy (Arm 1) is established, then the dose of MK-1454 in Arm 2 may continue escalation up to that established dose.

For Arm 3, dose escalation will proceed by incrementing dose frequency then dosage level. The initial dose frequency of visceral IT will be collected. Per mTPI design, frequency will increase in the next cohort to collected for 2 cycles, followed by thereafter. Further increase in visceral IT injection frequency to collected for 2 cycles, followed by thereafter in a subsequent cohort will be based on mTPI design. After Cycle 3, the frequency of visceral IT administration may be modified based on clinical assessment of safety by the investigator in consultation with Sponsor. Dose decisions will be made jointly with the investigators. Enrollment into Arm 3 will be monitored through IWRS.

Protocol/Amendment No.: 001-08

Table 10 Dose-finding Rules per mTPI Design

	Num	Number of subjects evaluable for DLT at current dose										
Number of subjects with at												
least 1 DLT	3	4	5	6	7	8	9	10	11	12	13	14
0	Е	Е	Е	Е	Е	Е	Е	Е	Е	Е	Е	E
1	S	S	S	Е	Е	Е	Е	Е	Е	Е	Е	E
2	D	S	S	S	S	S	S	S	Е	Е	Е	E
3	DU	DU	D	S	S	S	S	S	S	S	S	S
4		DU	DU	DU	D	D	S	S	S	S	S	S
5			DU	DU	DU	DU	DU	D	S	S	S	S
6				DU	DU	DU	DU	DU	DU	D	S	S
7					DU	D						
8						DU						
9							DU	DU	DU	DU	DU	DU
10								DU	DU	DU	DU	DU
11									DU	DU	DU	DU
12										DU	DU	DU
13											DU	DU
14												DU

D = De-escalate to the next lower dose

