5.2.2 Definition of Dose-Limiting Toxicity

Dose-limiting toxicities will be defined from toxicities observed during the first cycle of treatment (21 days) for each dose level. See Section 5.9 for rules on replacement of subjects in the DLT period.

Subjects who experience a DLT in Cycle 1 will be discontinued from treatment. However, if in the opinion of the investigator the subject is deriving clinical benefit from the study treatment (for example a marked reduction in tumor burden), the subject may be allowed to continue on the study at a reduced dose level of MK-1454 upon resolution of the DLT to a ≤ Grade 1 AEs or to baseline, and upon discussion with the Sponsor Therefore, flexibility of rechallenge of MK-1454 at a lower dose per dose modification guidance below subsequent to a DLT may be considered.

The occurrence of any of the following toxicities during Cycle 1, if assessed by the investigator to be related, probably related, or possibly related to the drug will be considered a DLT, excluding toxicities clearly not related to the drug, such as disease progression, environmental factors, unrelated trauma, etc.:

1. Grade 4 nonhematologic toxicity (not laboratory)

DU = The current dose is unacceptably toxic

E = Escalate to the next higher dose

S = Stay at the current dose

Target toxicity rate = 30%

Flat non-informative prior Beta (1,1) is used as a prior and $\varepsilon 1=\varepsilon 2=0.03$ [31] [34]

Protocol/Amendment No.: 001-08

2. Grade 4 hematologic toxicity lasting ≥7 days, except thrombocytopenia

- a. Grade 4 thrombocytopenia of any duration
- b. Grade 3 thrombocytopenia is a DLT if associated with clinically significant bleeding
- 3. Any nonhematologic AE ≥ Grade 3 in severity should be considered a DLT, with the following exceptions: Grade 3 fatigue lasting ≤3 days; Grade 3 nausea, vomiting, or diarrhea lasting ≤3 days in the absence of antiemetics or antidiarrheals per standard of care; Grade 3 rash without use of corticosteroids or anti-inflammatory agents per standard of care; Grade 3 fever and Grade 3 flu-like symptoms lasting ≤24 hours with negative infectious disease workup (including negative blood and urine cultures)
- 4. Any Grade 3 or Grade 4 nonhematologic laboratory abnormality, if
 - medical intervention is required, or
 - the abnormality leads to hospitalization, or
 - the abnormality persists for >1 week
- 5. Febrile neutropenia Grade 3 or Grade 4

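### The mTPI enrolment cap is counted from a fixed cell (1 DLT in 3) instead of the current cell, so as written it allows one pending subject too many at five Stay cells and is tighter than its own logic needs at most others

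*Combined protocol and SAP*

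**What the plan says.** Section 5.2.1.3 gives the purpose of the rule: "The number of subjects who are enrolled at each dose is capped to minimize the exposure to a dose that may be unacceptably toxic". The next sentence is the general instruction for finding the number of further subjects. The reader is to "count steps in a diagonal direction (down and to the right) from the cell (3 subjects, 1 DLT) to the first cell marked DU".

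A worked example follows. With 1 DLT among 3 subjects, "then no more than an additional 3 subjects should be enrolled at this dose level until additional DLT data are available", because three more DLTs would make the dose unacceptably toxic ("ie, 4/6 subjects with DLT in Table 10").

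Earlier in the same section, after the decisions for cohorts of three have been described, the text adds: "The same principle will be applied whether 3, 4, 5 or 6 subjects are initially enrolled in the same dose cohort according to Table 10". No other section gives a count for any other combination of subjects and DLTs.

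Table 10 contains the decisions: E (escalate), S (stay), D (de-escalate) and DU (unacceptably toxic). Its columns are headed as subjects evaluable for DLT, whereas the text of 5.2.1.3 describes them as patients treated.

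**The concern.** The cap is a worst-case rule. If every further subject had a DLT, how many could be treated before the table reads DU? The answer depends on where the dose level stands now. The instruction fixes the start at 1/3, so it returns 3 whatever has been observed.

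An enrolment system or site that follows the sentence as written would apply 3 at every Stay cell. The affected cells include 2/4 and 3/6, which can arise directly from permitted starting cohorts of 4 and 6. At these cells the observed DLT rate is 43% to 50% against a 30% target, so they are where the safeguard matters most. At many other cells the same sentence would hold back enrolment that the cap's reasoning would allow.

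**Working it through.** **Inputs.** Table 10, the cap sentence and its example (5.2.1.3); target DLT rate 30%, tolerance 3%, Beta(1,1) prior (5.2.1.3 and Table 10 footnotes); maximum of 14 subjects per dose level (5.2.1.3). Cells are written DLTs/subjects. One diagonal step adds one subject and one DLT.

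**Step 1: reproduce the plan's figure.** From 1/3: 2/4 is S, 3/5 is D, 4/6 is DU. That is 3 steps, as the plan states.

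**Step 2: check the table.** The decision was recomputed as the interval (below 0.27, 0.27 to 0.33, above 0.33) with the largest posterior probability per unit length under Beta(1 + DLTs, 1 + subjects − DLTs). DU was assigned when P(rate > 0.30) exceeds a cutoff. The documents do not state the cutoff. A value of 0.95 reproduces all 78 printed cells in the rows for 0 to 6 DLTs, and 0.90 misses 7 of them, so 0.95 is an assumption recovered from the table.

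The row for 7 DLTs is broken in the text we have. With the 0.95 cutoff:
- 7/13: P(rate > 0.30) = P(Binomial(14, 0.30) ≤ 7) = 0.969, so DU.
- 7/14: P(Binomial(15, 0.30) ≤ 7) = 0.94999, so just short of DU. The decision is D, which agrees with the D still visible at the end of that row.

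**Step 3: count from the current cell.**

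| Current cell | Path | Steps to DU | Written cap |
|---|---|---|---|
| 2/4 | 3/5 D, 4/6 DU | 2 | 3 |
| 3/6 | 4/7 D, 5/8 DU | 2 | 3 |
| 3/7 | 4/8 D, 5/9 DU | 2 | 3 |
| 4/9 | 5/10 D, 6/11 DU | 2 | 3 |
| 5/11 | 6/12 D, 7/13 DU (reconstructed) | 2 | 3 |
| 1/3, 2/5, 2/6, 3/8, 4/10 | – | 3 | 3 |
| 1/4, 1/5, 2/7, 3/9 | – | 4 | 3 |
| 2/8 | – | 5 | 3 |
| 12 other S cells | no DU cell by 14 subjects | – | 3 |

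The counts for 5/11, 4/10, 3/9 and 2/8 pass through the reconstructed 7/13 cell. The first four rows use legible cells only.

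**Step 4: tally.** There are 27 S cells with 3 to 13 subjects. By number of DLTs from 1 to 6 they number 3 + 7 + 8 + 5 + 3 + 1 = 27. The written cap is too loose by one in 5, equal in 5, and stricter than needed in 5 + 12 = 17. Nine of those 17 have 11 to 13 subjects, where the maximum of 14 leaves at most three places anyway. The fixed count therefore actually holds enrolment back in 17 − 9 = 8.

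**Step 5: what the extra subject means.** Take 3/6 with three subjects pending. If the first two results are both DLTs, the cell becomes 5/8 = DU while the third subject is already on treatment. For an assumed true DLT rate p, that chance is p²: 0.30² = 9%, 0.50² = 25%, 0.60² = 36%.

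**The case against.** The strongest reply is that nobody would read the sentence literally. An instruction to count is pointless if the answer is always 3, the example that follows uses 1/3, and the reason given for it makes sense only from the current state. The authors very probably meant the current cell. That stands as a reading of intent. However, the fixed cell sits in the rule itself, before the example begins, and no other text supplies a count for other states, so the operative sentence still gives the wrong number.

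It is also fair that the literal rule is conservative more often than it is loose, and that the excess is never more than one subject at a time.

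Two stronger readings are tempting, and the documents do not support either.

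- A reader might infer that subjects may be treated at a dose already classed as unacceptably toxic. The extra subject starts while the table reads S. DU becomes known only afterwards, and nothing in the rule permits dosing after that.
- A reader might infer that starting six subjects breaks the cap, because 3/3 is already DU and the first two subjects need be only 7 days apart. But 5.2.1.3 separately provides that "there may be a minimum of 3 and up to 6 subjects enrolled within 21 days of initiation at each new dose level", and sections 2.1.1 and 8.9.1 repeat the 3-to-6 cohort size. The cap concerns how many more may be enrolled once data exist, and Table 10 has no column below three subjects. The initial cohort size is a stated design choice. It is accompanied by the stagger between the first two subjects, at least 24 hours of observation after the first dose, and weekly safety calls.

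**Conclusion.** The cap sentence in 5.2.1.3 is wrong as a general rule and right for its own example. Taken literally, it allows one pending subject too many in 5 of 27 Stay cells, is correct in 5, and is stricter than needed in 17. Four of the five loose cells are read directly from the printed table. The fifth, 5/11, rests on a reconstructed cell and the assumed 0.95 cutoff.

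The error does not invalidate Table 10 or any dose decision taken from it, and it does not show that the safeguard fails overall. Section 4.2.2.5 reports that the dose for Cohorts A and B has already been selected, so what remains at stake is mainly Arm 3, from which the Cohort C dose and frequency are to be taken. The correction is worth making because the sentence governs enrolment at a dose level and costs almost nothing to put right.

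**What to change.** In 5.2.1.3, replace the fixed start cell with *the current cell (number of subjects evaluable, number with a DLT)* and keep 1/3 as the worked example.

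Add one sentence on pending subjects. Section 5.2.2 states: "Dose-limiting toxicities will be defined from toxicities observed during the first cycle of treatment (21 days) for each dose level". A subject treated but still inside that window should therefore use up one of the places the cap allows. This would also settle whether Table 10 columns mean treated or evaluable subjects.

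At most, add a clause saying that the cap applies to enrolment after the initial cohort of 3 to 6, so that the two provisions are not read against each other.

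The cost is two or three sentences and a matching check in the IWRS. Table 10 and the sample size do not change. Correcting the start cell tightens the cap by one subject at five cells and loosens it in the eight where the fixed count was needlessly holding enrolment back.

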- 19. Has a history of re-irradiation for HNSCC at the projected injection site.
- 20. Has a tumor(s) in direct contact or encases a major blood vessel, and has ulceration and/or fungation onto the skin surface at the projected injection site.
- 21. HIV-infected subjects with history of Kaposi's sarcoma and/or multicentric Castleman's disease.
- 22. HIV-infected subjects who have had an HIV-related opportunistic infection within 6 months.

Protocol/Amendment No.: 001-08

23. Drug-drug interactions have to be taken into consideration and decisions whether a particular drug can be used as a concomitant medication in the study should be based on recommendations at the time of the study and depending on the MOA of the study drug. Patients on ART agents with a potentially significant overlapping toxicity profile should be excluded if the therapy cannot be switched to the regimen without overlapping toxicity.

5.1.4.2 Exclusion Criteria for Crossover Into Arm 2

The subject must be excluded from crossover into Arm 2 of the trial if the subject:

- 1. Has had chemotherapy, definitive radiation, or biological cancer therapy within 4 weeks (2 weeks for palliative radiation) prior to the first dose of study therapy, or has not recovered to baseline or CTCAE Grade 1 (Grade 2 alopecia is allowed) from the AEs due to cancer therapeutics administered more than 4 weeks earlier.
- 2. Is currently participating and receiving study therapy or has participated in a study of an investigational agent and has received study therapy or has used an investigational device within 28 days of administration of MK-1454.

Note: Prior exposure to MK-1454 is allowed, provided the patient has a washout period of at least 14 days and did not experience Grade 3 or higher drug-related toxicity.

Note: Prior exposure to immunotherapeutics is allowed, including PD-1 and PD-L1 inhibitors, provided patient did not experience $a \ge Grade 3$ drug-related toxicity on monotherapy with a PD-1 or PD-L1 inhibitor

- 3. Is expected to require any other form of antineoplastic therapy while on study.
- 4. Is on chronic systemic steroid therapy in excess of replacement doses (prednisone $\leq 10 \text{ mg/day}$ is acceptable), or on any other form of immunosuppressive medication.

Note: The use of physiologic replacement doses of corticosteroids may be approved after consultation with the Sponsor Medical Monitor.

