result and known quantitative HCV RNA results greater than the lower limits of detection of the assay.

- 16. HIV-infected subjects with history of Kaposi's sarcoma and/or multicentric Castleman's disease.
- 17. HIV-infected subjects who have had an HIV-related opportunistic infection within 6 months.
- 18. Drug-drug interactions have to be taken into consideration and decisions whether a particular drug can be used as a concomitant medication in the study should be based on recommendations at the time of the study and depending on the MOA of the study drug. Patients on ART agents with a potentially significant overlapping toxicity profile should be excluded if the therapy cannot be switched to the regimen without overlapping toxicity.
- 19. Has been treated with a STING agonist (eg, MK-1454, ADU-S100).
- 20. Has a history or current evidence of any condition, therapy, or laboratory abnormality that might confound the results of the study, interfere with the subject's participation for the full duration of the study, would make administration of the study drugs hazardous or make it difficult to monitor adverse effects such that it is not in the best interest of the subject to participate, in the opinion of the treating investigator.
- 21. Has known psychiatric or substance abuse disorders that would interfere in cooperation with the requirements of the trial.
- 22. Is pregnant or breastfeeding or expecting to conceive or father children within the projected duration of the study.
- 23. Has not fully recovered from any effects of major surgery and be free of significant detectable infection. Surgeries that required general anesthesia must be completed at least 2 weeks before first study drug administration. Surgery requiring regional/epidural anesthesia must be completed at least 72 hours before first study drug administration and subjects should be recovered.
- 24. Has received a live vaccine within 30 days prior to first dose.
- 25. Has a history of re-irradiation for SCCHN at the projected injection site in the head and neck.
- 26. Has a tumor(s) in direct contact or encases a major blood vessel and has ulceration and/or fungation onto the skin surface at the projected injection site in the head or neck.
- 27. Has experienced weight loss >10% over 2 months prior to first dose of study therapy.

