8.6.2 Statistical Methods for Safety Analyses

Safety and tolerability will be assessed by clinical review of all relevant parameters including AEs, SAEs, laboratory tests, vital signs, ECG measurements, and physical examinations.

MK-1454-001-08 Final Protocol 27-Jul-2021 Confidential

Protocol/Amendment No.: 001-08

AEs will be summarized by counts and frequencies for each dose level, arm, and cohort. Laboratory tests, vital signs, and other safety endpoints will be summarized as appropriate.

Dose-limiting toxicities will be listed, and further summarized by dose level and arm. The pool adjacent-violators-algorithm [31], which forces the DLT rate estimates to be nondecreasing with dose levels and pools adjacent violators for weighted estimates by sample size, will be used to estimate the DLT rates across doses in each treatment arm. The estimates of the DLT rates among subjects treated at the MTDs (or MADs) and the 80% Bayesian credible intervals based on a prior distribution of Beta (1,1) for the estimates will be provided.

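### The pooled Arm 2 DLT rate may understate the rate in MK-1454-naive subjects, and Section 8.6.2 plans no split by prior exposure that would show it

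*Combined protocol and SAP*

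**What the plan says.** **Who can be in the cohort.** Section 5.2.1.3 "requires that at least half of the 14 subjects in the MTD/MAD cohort have had no prior exposure to MK-1454"; Section 2.1.1 has the same rule. Section 5.2.1.3 adds: "Priority for enrollment in the MTD/MAD confirmation cohort of Arm 2 will be given to MK-1454-naïve subjects". Both rules concern the MTD/MAD cohort. Neither section limits crossovers at the other Arm 2 dose levels, where Table 10 gives decisions from 3 subjects upward.

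**How crossovers are screened.** Under Section 5.1.4.2, earlier MK-1454 is acceptable "provided the patient has a washout period of at least 14 days and did not experience Grade 3 or higher drug-related toxicity".

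**How DLTs are analysed.** DLT is a primary endpoint (Sections 8.1 and 8.4.2). The DLT-evaluable set in Section 8.5.1 does not distinguish subjects by prior MK-1454 exposure. Section 8.6.2 summarises DLTs by dose level and arm and plans "The estimates of the DLT rates among subjects treated at the MTDs (or MADs) and the 80% Bayesian credible intervals".

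**Where the Arm 2 result goes.** Cohorts A and B start at the preliminary RP2D from Arm 2 (Sections 2.1.2 and 4.2.2.6). Exclusion criterion 19 of Section 5.1.5 begins "Has been treated with a STING agonist (eg, MK-1454, ADU-S100", so no Part II subject has had MK-1454 before. Cohort C takes its dose and frequency from Arm 3.

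**The concern.** Most DLT criteria in Section 5.2.2 are drug-related events of Grade 3 or worse. Section 5.1.4.2 keeps out of crossover anyone who has already had such an event on MK-1454. Section 5.2.2 also takes most subjects with a Cycle 1 DLT off treatment. Crossovers have therefore already passed a tolerance screen on the same drug, and their DLT risk in Arm 2 may be lower than that of a naive subject.

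If so, the pooled Arm 2 estimate is a mixture that sits below the rate in naive subjects, and its credible interval describes a population that Cohorts A and B do not enrol. The half-naive rule and the priority for naive subjects show that the plan regards prior exposure as relevant. The analysis section does not carry this through, so a reader of the planned tables could not tell whether the DLTs clustered in the naive subjects.

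**Working it through.** **Inputs from the documents.** Target DLT rate 30% and tolerance 3%, so the stay interval is 27% to 33% (Section 5.2.1.3, Table 10). Flat Beta(1,1) prior for decisions and for reporting: "80% Bayesian credible intervals based on a prior distribution of Beta (1,1) for the estimates will be provided" (Section 8.6.2). Cohort of 14, of whom at least 7 are naive, so at most 14 − 7 = 7 crossovers.

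**Not in the documents.** The DLT rate in either group and the number of crossovers. Both are assumed below, over a range.

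**Step 1: reproduce Table 10.** With x DLTs in n subjects the posterior is Beta(1+x, 1+n−x). For each interval (below 27%, 27–33%, above 33%), divide the posterior mass by the interval length and take the largest. Mark DU if P(rate > 30%) exceeds 0.95. The 0.95 cut-off is my assumption: 0.95 gives no mismatches and 0.90 gives eight. All 78 cells for 0 to 6 DLTs match, as does 7 of 14 = D. At n = 14 the rule is E for 0–2, S for 3–6, D for 7 and DU for 8 or more.

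**Step 2: an example that needs no assumed rate.** Suppose there are 4 DLTs in 14 subjects, all among the 7 naive ones.
- Pooled: 4/14 = 28.6%. Beta(5,11) gives an 80% interval of 17.2% to 46.4%. Table 10 reads S.
- Naive only: 4/7 = 57.1%. Beta(5,4) gives 34.5% to 76.0%. Table 10 reads D.

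Similarly, 5/14 reads S while 5/7 reads DU. The planned summary would show only the 14-subject line.

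**Step 3: possible size.** Let p be the naive rate and q the crossover rate. With 7 of each, the pooled true rate is (7p + 7q)/14, and the DLT count X is the sum of Bin(7, p) and Bin(7, q):

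P(X ≥ 7) = Σ over i + j ≥ 7 of C(7,i) pⁱ(1−p)⁷⁻ⁱ × C(7,j) qʲ(1−q)⁷⁻ʲ

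Check with all 14 naive at 40%: for X = 7, 8, … the terms are 0.1574 + 0.0918 + 0.0408 + 0.0136 + 0.0033 + 0.0005 + 0.0001 = 0.3075.

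Naive rate 40%, 7 crossovers:

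| Crossover rate | Pooled true rate | P(0–2), E | P(3–6), S | P(7 or more), D or DU |
|---|---|---|---|---|
| 40% (no difference) | 40% | 4.0% | 65.3% | 30.8% |
| 30% | 35% | 8.3% | 73.5% | 18.2% |
| 20% | 30% | 15.4% | 75.8% | 8.8% |
| 10% | 25% | 26.3% | 70.9% | 2.8% |

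Varying the naive rate, with crossovers at half of it, P(X ≥ 7) goes from 9.3% to 2.0% (naive 30%), 60.5% to 23.4% (50%) and 85.0% to 45.2% (60%). With only 3 crossovers (naive 40%, crossover 20%) it goes from 31% to 20%.

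**Step 4: the naive rate behind an on-target pooled rate.** With 7 crossovers and rate ratio r = q/p, a pooled 30% means p = 0.30/(0.5 + 0.5r). This gives 34.3% (r = 0.75), 40% (0.5), 48% (0.25) and 60% (0).

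**Limit of the calculation.** Step 3 looks once, at n = 14. Table 10 also applies at smaller n, so these are not operating characteristics of the design.

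**The case against.** The other side has several good points.

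- **The bias is not shown.** Crossovers tolerated monotherapy, while the Arm 2 DLT question concerns the combination, and they have progressed on treatment. The documents give neither their DLT rate nor their number. This stands, so the claim has to be that the pooled rate may understate the naive rate.
- **Seven crossovers is a ceiling.** Naive subjects have priority. This stands, and the effect shrinks with fewer crossovers.
- **Earlier looks matter.** Under steeper assumed rates (naive 45%, crossover 15%), the single-look figures are 45% for all naive and 8% for the mixture. With assumed looks at 3, 6, 9, 12 and 14, the chance of D or DU at any look is 65% for all naive. For the mixture it is 49% with naive subjects first, 33% alternating and 13% with crossovers first. This stands: the gap depends heavily on enrolment order.
- **There are other protections.** Arm 2 doses stay at least two levels behind monotherapy and may not exceed its MTD. Safety is primary in Part II, with adverse events summarised by cohort, and Cohorts A and B can supply up to 60 naive subjects on the combination. This lowers the stakes but does not make the Arm 2 estimate itself transparent.
- **The dose is already chosen.** Section 2.1.2 calls the RP2D confirmed, and Section 4.2.2.5 bases it on safety, pharmacodynamic and early efficacy data. This also stands, so the change serves reporting and interpretation.

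A reader might go further and infer that the pooled Arm 2 DLT rate is applied to all Part II cohorts, or that the RP2D is biased. The documents do not support either. What carries forward is a dose chosen on composite data, which Section 2.1.1 allows to differ from the MTD/MAD. It goes only to Cohorts A and B; Cohort C, 60 of the 120 Part II subjects, is linked to Arm 3. Nor can the naive-only estimate now be named as the one supporting the RP2D, since that would recast a decision made on broader grounds.

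**Conclusion.** The point holds as a reporting gap in a primary safety estimate. Up to half of the Arm 2 MTD/MAD cohort may be subjects screened for tolerance of MK-1454, with no stated limit at other Arm 2 dose levels. Their DLTs are pooled with those of naive subjects, and nothing planned separates the two. The pooled rate and interval may therefore understate the rate in the kind of subject that Cohorts A and B enrol.

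The size cannot be established from the documents. It ranges from nothing, if the rates are equal, to the figures in the table, which assume a naive rate of 40%, the full 7 crossovers and a single look at n = 14. The 4/14 example does not depend on assumed rates, but it shows what the planned summary could hide, not what happened. This is a cheap improvement. It does not show that the mTPI rules or the chosen dose are at fault.

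**What to change.** In Section 8.6.2, add that Arm 2 DLTs will be summarised by prior MK-1454 exposure (naive or crossover) at each dose level. Report the naive-only DLT rate with its 80% credible interval, under the same Beta(1,1) prior, as a sensitivity estimate beside the pooled one. Refer to both when interpreting the Arm 2 MTD/MAD and the safety basis of the RP2D for Cohorts A and B. Enrolment rules, mTPI rules and doses are unchanged.

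The cost is a sentence or two of SAP text and one extra table; crossover status is already known. The drawback is a wide naive-only interval when there are as few as 7 naive subjects. For example, 2/7 gives Beta(3,6) and 15% to 54%, against 17% to 46% for a pooled 4/14. That width is a fair picture of how little Arm 2 may say about naive subjects, and the table should carry that caution.
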